2. Patients undergoing concomitant hiatal hernia repair or ventral hernia repair or cholecystectomy at time of primary metabolic surgery
3. Patients with chronic opioid use

Sample Size

The number of patients required in each group is determined from a power analysis based on primary hypothesis.

In this study, based on our clinical experience, we assume standard deviation for each group is 3, the margin of equivalence is 1.5 on NRS, and the true difference between the two groups is 0 on the NRS. Group sample size of 88 from each group achieves 90% power to detect our prespecified equivalence margins, with alpha of 0.05. Assuming a 20% dropout or withdrawal based upon previous experience, 106 subjects per group will be required.

Interventions and Interactions

There will be two groups: (1) active control and (2) study group. Active control group patients receive TAP block with a Bupivacaine only mixture, containing 50 mL 0.5% Bupivacaine, and 100 mL normal saline solution. Study group patients will receive TAP block with a Liposomal Bupivacaine mixture, containing 20 mL Liposomal Bupivacaine, 30 mL 0.5% Bupivacaine, and 100 mL normal saline solution. TAP block technique will be standardized using subcostal as well as anterior axillary line as landmarks, injecting down to level of T10, using laparoscopic-guided approach. TAP block will be administered at the start of every case, after the first port is placed upon laparoscopy. Type of anesthesia administered will also be standardized including the use of narcotics, lidocaine, inhalational anesthesia and Ketamine.

Randomization schedules will be generated by SAS 9.4 (SAS Institute Inc., Cary, NC) by using a masked block randomization procedure. Eligible patients will be randomized with a 1:1 ratio between the 2 groups of patients receiving TAP block Exparel mixture or simply bupivacaine administered via TAP block. Research Electronic Data Capture (REDCap) randomization

module will be used to manage randomization and allocate treatment groups. The allocation sequence will be concealed with application of the REDCap.

Outcome Measure(s)

Primary Outcome measures

1. Pain score at 24 hours post-operative, using visual analogue scale (VAS), ranging from 1 to 10. One indicates no pain, and 10 indicates the worst pain one could image.

Secondary Outcome Measures

1. Pain scores at 12 hours, 48 hours, and 72 hours post-operatively.
2. Morphine milligram equivalences consumed during hospital stay

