3. Morphine milligram equivalences prescribed and consumed as measured at one week follow up clinic visit
4. Post-operative nausea and vomiting (PONV) measured by a numerical score (1: no nausea or vomiting, 2: some nausea no vomiting, 3: nausea and vomiting)
5. Length of stay in hours
6. Patient satisfaction score

These parameters will be scored via SeamlessMD on a phone application, as well as paper and pen on a standardized reporting form for patients less comfortable using technology. Data will also be collected from patient electronic charts.

Analytical Plan

Equivalency test with priori specified non-inferiority region will be used to assess primary outcome variables.

Descriptive statistics (mean, range, percentage, median, etc.) will be used to assess the quality and accuracy of the administrative and clinical data. Means with standard deviations or medians with interquartile range (IQR) will be reported for continuous variables and percentages for categorical variables. Missing data will be evaluated prior to data modeling. General linear regression, or other generalized linear regression models will be used to compare the outcomes between the two groups with both univariate or multivariate analyses. Potential confounders will be identified with univariate analysis. For univariate analyses, a Student's t-test or Wilcoxon two-sample test will be used for continuous variables, and chi-square test for categorical variables against the primary and secondary outcomes. Both unadjusted and adjusted odds ratio (OR) with

corresponding 95% confidence interval (CI) will be reported. Two-tailed p values will be calculated for all tests, and $p < 0.05$ is considered statistically significant. All data will be analyzed using Statistical Analysis Software, version 9.4 (SAS Institute Inc., Cary, NC).

There are no plans for interim data analyses. Analyses will be conducted according to per-protocol (PP) principle.

Human Subjects Protection

Subject Recruitment Methods

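### Covariates are to be picked from the trial's own data, and neither the result nor the CI level that decides equivalence is named; pre-state one mean-difference rule with a 90% CI within ±1.5

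*Combined protocol and SAP*

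**What the plan says.** All of this is in the combined protocol and SAP.

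- **Primary test (Analytical Plan).** "Equivalency test with priori specified non-inferiority region will be used to assess primary outcome variables". No estimator, covariate set or CI level is attached.
- **Models (Analytical Plan).** Linear or generalized linear models are to be used "to compare the outcomes between the two groups with both univariate or multivariate analyses". The primary outcome is not excepted.
- **Covariates (Analytical Plan).** "Potential confounders will be identified with univariate analysis". There is no candidate list and no entry threshold. The next sentence says that a t-test or "Wilcoxon two-sample test will be used for continuous variables, and chi-square test for categorical variables against the primary and secondary outcomes".
- **Reporting (Analytical Plan).** "Means with standard deviations or medians with interquartile range (IQR) will be reported for continuous variables". For effects: "Both unadjusted and adjusted odds ratio (OR) with" "corresponding 95% confidence interval (CI) will be reported". All tests are to have two-tailed p values, judged at 0.05.
- **Hypothesis and size.** The Primary Hypothesis concerns the difference in population mean VAS at 24 hours, with δ = 1.5. The Sample Size section assumes SD 3 per group, margin 1.5, true difference 0 and alpha 0.05, and uses no covariates: "Group sample size of 88 from each group achieves 90% power".

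**The concern.** The trial is randomised 1:1 and ends in one yes-or-no verdict on equivalence. An equivalence test can be run on an unadjusted difference or on an adjusted model estimate, and against a 90% or a 95% interval. These can give different answers on the same data. The plan leaves the choice open and lets the adjusted model depend on the data.

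The sentence on testing variables against the outcomes can be read in two ways. Either covariates are screened for association with the outcome, or the named tests compare the arms. Under both, the adjusted model would be settled after the data are seen. At stake are the error rate of the equivalence claim, the power actually delivered, and a stated effect measure for the numeric outcomes.

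**Working it through.** **Inputs from the documents:** SD 3 per group, margin 1.5, true difference 0, alpha 0.05, 88 per group (Sample Size); difference in mean 24-hour VAS (Primary Hypothesis).

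**1. Reproduce 88 per group.** Take two one-sided tests (TOST) at 0.05 per side, which is the same as a 90% CI wholly within ±1.5.

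- Normal approximation: n = 2 × [3 × (1.645 + 1.645) / 1.5]² = 86.6, so 87.
- Exact t-based power: 0.899 at 87 and 0.903 at 88. So 88 is the smallest n that reaches 90%.
- Hand check: SE = 3 × √(2/88) = 0.452. The 90% half-width is 1.654 × 0.452 = 0.748. The estimate must lie within ±(1.5 - 0.748) = ±0.752. Power ≈ 2Φ(0.752/0.452) - 1 ≈ 0.90.

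The plan's figure is reproduced by an unadjusted TOST with a 90% CI.

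**2. The same design with a 95% CI.** The half-width is 1.974 × 0.452 = 0.893, so the estimate must lie within ±0.607. Power ≈ 2Φ(0.607/0.452) - 1 ≈ 0.82 (exact 0.819). Reaching 90% would take 105 per group.

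**3. The one-sided form written in the Primary Hypothesis.** At 0.05 it reaches 0.903 power with 70 per group and 0.951 with 88. So 88 matches the equivalence design and not the hypothesis as written.

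**4. False equivalence when covariates are selected from the data.** Simulation, 88 per arm, true difference 1.5, 40,000 trials per scenario (standard error about 0.11 points). The documents give no candidates, correlations or thresholds, so all of these are assumptions. Entry is at p<0.05.

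| Candidates, correlation with pain | Unadjusted | Screened on outcome | Screened on arm imbalance | Fixed in advance |
|---|---|---|---|---|
| 3, r = 0.15 | 4.8% | 5.2% | 4.6% | 4.7% |
| 8, r = 0.15 | 5.2% | 6.6% | 4.8% | 5.2% |
| 3, r = 0.10 | 5.0% | 5.4% | 4.9% | 4.9% |
| 8, r = 0.10 | 4.8% | 5.9% | 4.8% | 4.9% |
| 3, r = 0 | 4.8% | 4.9% | 4.8% | 4.8% |
| 8, r = 0 | 5.0% | 5.3% | 5.0% | 5.0% |

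A separate run of 20,000 trials at r = 0.15 gave 5.5% (3 candidates) and 6.2% (8) for outcome screening. If equivalence may be claimed when either the unadjusted or the outcome-screened result passes, that run gave 6.3% and 7.5%.

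**5. Disagreement between verdicts** (8 candidates, r = 0.15). The outcome-screened model disagrees with the unadjusted verdict in 6.2% of trials at true difference 0 and in 14.2% at 0.75. A fully prespecified adjusted model disagrees in 6.9% and 15.9%.

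**6. Power forgone by staying unadjusted.** With k uncorrelated covariates at r = 0.15, the residual SD is 3 × √(1 - k × 0.0225): 2.97 for k = 1, 2.90 for k = 3, 2.72 for k = 8. Power at 88 per group is then about 91%, 92% and 94-95%, against 90.3% unadjusted.

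**The case against.** The strongest defence is that the deciding test can be inferred. The equivalence sentence opens the Analytical Plan, the hypothesis is about means, and the sample size has no covariates and reproduces as an unadjusted TOST. Regression and confounders come later, in general text. On that reading nothing is inflated. The inference is reasonable, but the plan never says so, and the only CI level it states is not the one that yields its power.

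A second defence is that outcome screening fits the named tests poorly. A two-sample t-test or Wilcoxon test cannot relate a continuous covariate to numeric VAS, and chi-square cannot relate a categorical covariate to VAS unless VAS is cut into categories. This stands. Comparing the arms is the easier reading, and screening on imbalance does not inflate the error.

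Four stronger conclusions might be inferred, and the documents do not support them:

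- **That the plan seriously inflates false equivalence.** This needs outcome screening, that model (or either result) deciding, and several prognostic candidates. None of these is stated.
- **That the disagreement rates show harm from screening.** Prespecified adjustment disagrees with the unadjusted verdict just as often. The rates support only naming one analysis.
- **That only an unadjusted analysis is valid.** A model with covariates fixed in advance also controls error and can add power.
- **That equivalence will be tested on an odds ratio.** The hypothesis is on means, and a general linear model estimates mean differences. What is missing is a statement that those differences and their intervals will be reported.

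**Conclusion.** The point holds in a limited form. The plan selects covariates from trial data, promises unadjusted and adjusted results side by side, and does not say which result or CI level decides. The firmest consequence needs no outside assumption: at the plan's own inputs, moving from a 90% to a 95% CI lowers power from 90.3% to 81.9%.

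The error-rate consequence is modest and rests on assumptions. At correlation 0.15 and entry p<0.05, false equivalence is about 5 to 6.6% if an outcome-screened model decides and about 6 to 7.5% if either result may be used. There is no inflation under imbalance screening or if the unadjusted test decides. The change should be made because it is cheap and removes the ambiguity, not because the present wording is shown to do large harm.

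**What to change.** 1. Delete the sentence that has confounders identified by univariate analysis.
2. Before any outcome data are analysed, state one deciding rule. Only patients are described as blinded, so a deadline tied to unblinding would be unclear. Suggested text: *Equivalence is concluded if the 90% CI for the difference in mean 24-hour VAS (study minus control) lies wholly within -1.5 to +1.5, that is, two one-sided tests at 0.05 each.* State the analysis set in the same sentence; whether per-protocol alone is suitable is a separate question.
3. Say whether the difference is unadjusted or comes from a linear model with covariates fixed in advance, such as sleeve or bypass. Unadjusted is the natural default, because the sample size uses no covariates. Make the other a sensitivity analysis.
4. Exempt this test from the two-tailed p value and 95% CI wording, and reconcile the one-sided Primary Hypothesis with the equivalence design.
5. Report mean differences with CIs for numeric outcomes. Limit odds ratios to categorical outcomes such as PONV; its three ordered levels suit an ordinal model.

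The cost is wording only: no new data and no change in the 88 per group. Staying unadjusted forgoes some power, by an amount that depends on the covariates: 90.3% against about 91% with one, 92% with three and 94-95% with eight, at an assumed correlation of 0.15.

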- 1) Lower values of the outcome variable VAS are desirable, and the hypothesis is listed below –

Hypothesis 1. 1

$H_0: \mu_E - \mu_S \geq \delta$ (Study group is different compared to the active control group by δ or more)

$H_1: \mu_E - \mu_S < \delta$ (Study group is equivalent to the active control when difference is within prespecified δ)

Where μ_E, μ_S are the population means for the outcome VAS measured at 24 hours after surgery for the study group (E) and the standard (S) active group, respectively

δ is non-inferiority margin, specified in advance based on clinical judgement. Based on our clinical experience, $\delta = 1.5$

Secondary Objectives: Compared to TAP block with Bupivacaine only, we will compare opioid consumption, and other effect differences to patients undergoing metabolic and bariatric surgery receiving TAP block with Liposomal Bupivacaine.

Secondary Hypotheses

Hypothesis 2.1 – Patients undergoing metabolic and bariatric surgery receiving TAP block with Liposomal Bupivacaine results in less opioid consumption before hospital discharge /during the first 48 hours postoperatively as measured in morphine equivalents (mg) compared to patients receiving simply TAP block with Bupivacaine only.

Hypothesis 2.2 - Patients undergoing metabolic and bariatric surgery receiving TAP block with Liposomal Bupivacaine results in pain score as measured by visual analog scale (VAS) at 12 hours after surgery that are equivalent compared to patients receiving TAP block with Bupivacaine only.

Exploratory objectives: We will explore other effects, including pain score at 48 hours, and 72 hours after surgery, total opioid consumption required post op during their one-week post op visit as measured in morphine equivalences.

Methods and Measures

Design

This study is a 2-arm parallel single blinded randomized equivalency, single-center, clinical trial. Patients will be blinded to type of TAP block used.

Setting

This study will take place at Atrium Health, an academic medical center.

Subjects selection criteria

Inclusion Criteria

To be eligible for enrollment in this study, participants must meet all the following criteria:

1. Adult, age > 18 years
2. Participants who can give written informed consent and willing to comply with all stud-related procedures.
3. Patients undergoing primary sleeve gastrectomy or roux-en-y gastric bypass

Exclusion Criteria

1. Patients undergoing duodenal switch procedures

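### The primary equivalence rule is not written down: the blanket two-tailed 0.05 rule and the one-bound Hypothesis 1.1 both conflict with the test that 88 per group was sized for

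*Combined protocol and SAP*

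**What the plan says.** Four places in the protocol bear on how the primary conclusion will be reached.

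- **Primary Hypothesis, Hypothesis 1.1.** H0 is μE − μS ≥ δ and H1 is μE − μS < δ, with δ = 1.5 described as a non-inferiority margin. Only the upper bound is written, yet the gloss on H1 reads "Study group is equivalent to the active control when difference is within prespecified" δ.
- **Sample Size.** With SD 3, margin 1.5 and true difference 0: "Group sample size of 88 from each group achieves 90% power to detect our prespecified equivalence margins, with alpha of 0.05". The text does not say whether 0.05 is per side.
- **Analytical Plan, primary outcome.** "Equivalency test with priori specified non-inferiority region will be used to assess primary outcome variables". No procedure, level per side or interval for the mean VAS difference follows.
- **Analytical Plan, general rules.** Univariate analyses use a t-test or "Wilcoxon two-sample test will be used for continuous variables, and chi-square test for categorical variables against the primary and secondary outcomes". The only confidence interval, at 95%, belongs to odds ratios ("Both unadjusted and adjusted odds ratio (OR) with" their 95% CI). The section then says "Two-tailed p values will be calculated for all tests", with significance at p < 0.05 and no exception for the equivalence test.

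**The concern.** An equivalence conclusion needs one decision rule, fixed before the data are seen. The text can be followed in at least four ways:

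1. 90% CI inside ±1.5 (TOST at 5% per side).
2. 95% CI inside ±1.5 (TOST at 2.5% per side), if the two-tailed 0.05 rule is carried to the equivalence test.
3. Upper limit below +1.5 only, as Hypothesis 1.1 is written.
4. A two-tailed t or Wilcoxon p-value, which tests a zero difference and ignores the margin.

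These rules are not interchangeable. The second is stricter than the test the trial appears to have been sized for. The third lets a large benefit of the study group count as equivalence. The fourth cannot support equivalence at all, because failing to reject zero is not evidence that the difference is small. If the choice is left until analysis, it could decide the primary result.

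**Working it through.** **Inputs (Sample Size and Hypothesis 1.1):** SD 3 in each group, margin 1.5, true difference 0, alpha 0.05, 88 per group, 1:1 allocation.

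**Standard error at 88 per group:** SE = 3 × √(2/88) = 0.4523, with 174 degrees of freedom. Margin/SE = 1.5/0.4523 = 3.317.

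**Step 1. Reproduce the stated 90%.** For TOST with true difference 0, the normal approximation to power is 2Φ(margin/SE − z) − 1, where z is the one-sided critical value.

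- 5% per side: 2Φ(3.317 − 1.645) − 1 = 90.5%.
- 2.5% per side: 2Φ(3.317 − 1.960) − 1 = 82.5%.

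The exact version uses the t critical value and integrates over the distribution of the pooled SD. It gives 90.3% and 81.9%. The stated 90% is therefore reproduced at 5% per side and not at 2.5% per side.

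**Step 2. Find which rule gives 88 as its minimum.** The normal formula for 90% power is n = 2 × [SD × (z + 1.645)/margin]².

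- 5% per side: 2 × [3 × (1.645 + 1.645)/1.5]² = 86.6, so 87.
- 2.5% per side: 2 × [3 × (1.960 + 1.645)/1.5]² = 104.0, so 104.

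The exact minimum is one higher in each case. For the one-bound form, power comes from the noncentral t distribution with noncentrality 3.317.

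| Decision rule | Power at 88 per group | Minimum n per group for 90% |
|---|---|---|
| 90% CI inside ±1.5 | 90.3% | 88 (87 gives 89.9%) |
| 95% CI inside ±1.5 | 81.9% | 105 (104 gives 89.7%) |
| One bound, one-sided 2.5% | 91.0% | 86 |
| One bound, one-sided 5% | 95.1% | 70 |

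Of these four rules, only TOST at 5% per side has 88 as its minimum.

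**Step 3. What the choice does to a result.** With an observed SD of 3, the CI half-width is 0.748 at 90% and 0.893 at 95%. Equivalence is declared for an observed difference up to 1.5 − 0.748 = 0.752 under the 90% CI, and up to 1.5 − 0.893 = 0.607 under the 95% CI. Any trial that passes the 95% rule also passes the 90% rule. With true difference 0, the two therefore disagree in 90.3% − 81.9% = 8.4% of trials.

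**Step 4. The p-value against zero.** With the same SD, a two-tailed t-test gives p > 0.05 whenever the observed difference is below 0.893 in size. An observed difference between 0.752 and 0.893 would thus be non-significant against zero and still fail equivalence under the 90% CI.

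**Step 5. The one-bound form.** H1 in Hypothesis 1.1 is satisfied by every difference below +1.5, including differences below −1.5. Power is not lost, but the hypothesis no longer describes equivalence.

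**The case against.** The strongest reply is that the level can be recovered. The margin, alpha, true difference and n are all prespecified, and only TOST at 5% per side has 88 as its minimum. No sentence requires a 95% CI inside ±1.5, so 81.9% belongs to a rule the protocol never states. The two-tailed sentence closes a paragraph on descriptive, univariate and regression analyses, and most naturally refers to those. The design label, the glosses on H0 and H1 and the plural margins in Sample Size all point to two bounds.

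Much of this stands. The sample size of 88 is not wrong, the intended level can be inferred, and 81.9% is conditional on one reading. The reply does not remove the problem. The inference requires working back from n, while the only explicit significance rule in the analysis section covers all tests and does not match the inferred level. The formal hypothesis agrees with neither. The t-test or Wilcoxon test is also expressly directed at the primary outcome, and nothing says it may not be used to argue equivalence.

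**Conclusion.** The concern holds and should be fixed. The plan does not state the rule for its primary conclusion, and two things it does state would mislead if followed literally. Carrying the two-tailed 0.05 rule to a 95% CI inside ±1.5 lowers power at 88 per group from 90.3% to 81.9%. The one-bound Hypothesis 1.1 would label any advantage of the study group as equivalent.

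The figures rest on the protocol's own SD of 3, margin of 1.5 and true difference of 0, an equal-variance t analysis, and 88 evaluable patients per group. The evaluable number may differ, since 106 per group are to be enrolled. If 20% are lost, 106 × 0.8 = 84.8 remain. At 84 to 85 per group, power is 88.6% to 89.1% under the 90% CI and 79.3% to 80.0% under the 95% CI. With no losses, 106 per group gives 95.3% and 90.4%. At each of these sizes the 95% rule is the less powerful.

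**What to change.** In the Analytical Plan, state that:

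- equivalence is declared only if the 90% CI for the difference in mean 24-hour VAS (study minus control) lies entirely between −1.5 and +1.5 (TOST, 5% per side);
- the two-tailed p < 0.05 rule does not apply to this test;
- a test of zero difference will not be used to support equivalence.

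Rewrite Hypothesis 1.1 to match. H0: difference ≤ −1.5 or ≥ +1.5. H1: difference between −1.5 and +1.5. Keep two-tailed 5% tests for difference hypotheses such as 2.1.

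This costs one or two sentences and a rewritten hypothesis, with no extra patients. If the sponsor prefers a 95% CI, either restate power as about 82% at 88 per group or plan for 105 evaluable per group. Allowing for 20% dropout, that means enrolling 126 per group by the protocol's apparent method (88 × 1.2 gives its 106, and 105 × 1.2 = 126) or 132 by division (105/0.8 = 131.25).

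A side point, which the conclusion does not rest on: Hypothesis 2.2 also claims scores "at 12 hours after surgery that are equivalent compared to patients receiving TAP block with Bupivacaine only" but gives no margin for that time point. The same form of rule can be used there once the sponsor states one.

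### Per-protocol is the only analysis set: the opioid hypothesis and other difference outcomes have no as-randomised analysis, and the equivalence tests have no second set beside them

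*Combined protocol and SAP*

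**What the plan says.** The last sentence of the Analytical Plan reads "Analyses will be conducted according to per-protocol (PP) principle". It carries no qualification, so it covers every outcome. No intention-to-treat, full-analysis or other as-randomised set appears in the document. The deviations that would remove a patient are not listed.

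The outcomes are of two kinds:

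- **Equivalence.** The primary hypothesis concerns 24 h pain. Hypothesis 2.2 concerns pain "at 12 hours after surgery that are equivalent compared to patients receiving TAP block with Bupivacaine only".
- **Difference.** Hypothesis 2.1 is directional: the liposomal mixture "results in less opioid consumption before hospital discharge /during the first 48 hours postoperatively". One-week opioid use, nausea and vomiting, length of stay, satisfaction, and 48 h and 72 h pain have no equivalence hypothesis, so they fall under the plan's ordinary two-tailed comparisons.

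On blinding, the Design section says only "Patients will be blinded to type of TAP block used".

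**The concern.** The usual argument for a per-protocol set in an equivalence trial is that non-adherence can pull the arms together and make equivalence too easy to show. That argument does not carry over to a claim that one arm uses less opioid. There, dropping patients after randomisation means the groups compared are no longer those that randomisation formed.

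The estimate is biased when exclusion is related to outcome and either the exclusion rate or the strength of that relation differs between arms. Equal exclusion counts alone are therefore not reassuring.

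The documents leave room for such exclusions. One eligibility criterion depends on what is done in theatre: "Patients undergoing concomitant hiatal hernia repair or ventral hernia repair or cholecystectomy at time of primary metabolic surgery". The block, however, comes first: "TAP block will be administered at the start of every case, after the first port is placed upon laparoscopy". A patient could receive the block and then meet the criterion. Staff are not stated to be blinded and the exclusion rules are open, so outcome-related exclusion cannot be ruled out. With no as-randomised result, a reader could not tell whether exclusions shaped the opioid finding.

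**Working it through.** **Inputs from the documents.** SD 3 per group, margin 1.5, true difference 0, alpha 0.05, 88 per group for 90% power, 106 per group enrolled (Primary Hypothesis; Sample Size). Two-tailed p < 0.05 (Analytical Plan).

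**Inputs assumed.** The share p excluded in each arm, and the correlation ρ between exclusion and a worse outcome. The documents give neither.

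**The plan's own figure.** Two one-sided t-tests (TOST), each at 0.05, have exact power of 90.3% at 88 per group. This reproduces the stated 90%. At 106 per group the power is 95.3%.

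**Model.** There is no true difference, and the worst outcomes tend to be excluded.

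- Fall in an arm's mean, in SD units: ρ·φ(z)/(1−p), where z is the upper-p normal quantile. The slight fall in SD after exclusion is ignored.
- Retained n = 106(1−p), rounded.
- False rate: the chance that a two-sided 0.05 t-test favours the liposomal arm, from the noncentral t distribution. Without bias it is 2.5%.

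**One case in full: 5% of control and 10% of liposomal patients excluded, ρ = 0.5.**

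- Control: 0.5 × 0.1031/0.95 = 0.054 SD.
- Liposomal: 0.5 × 0.1755/0.90 = 0.097 SD.
- Net shift 0.043 SD, or 0.043 × 3 = 0.13 pain points.
- With 101 and 95 retained, the standard error is √(1/101 + 1/95) = 0.143 SD, so the noncentrality is 0.043/0.143 = 0.30 and the false rate is 4.9%.

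**All cases** (control value first, then liposomal):

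| Excluded | ρ | n | Shift, SD | Shift, pain points | TOST power, unbiased → shifted | False 'less opioid' rate |
|---|---|---|---|---|---|---|
| 5% v 10% | 0.3 both | 101, 95 | 0.026 | 0.08 | 93.4 → 93.0% | 3.8% |
| 5% v 10% | 0.5 both | 101, 95 | 0.043 | 0.13 | 93.4 → 92.2% | 4.9% |
| 10% v 20% | 0.3 both | 95, 85 | 0.046 | 0.14 | 90.9 → 89.4% | 4.9% |
| 10% v 20% | 0.5 both | 95, 85 | 0.077 | 0.23 | 90.9 → 86.6% | 7.4% |
| 20% v 20% | same in both | 85, 85 | 0 | 0 | 89.1% | 2.5% |
| 20% v 20% | 0.3 v 0.5 | 85, 85 | 0.070 | 0.21 | 89.1 → 85.4% | 6.6% |
| 10% v 10% | 0 v 0.5 | 95, 95 | 0.097 | 0.29 | 92.6 → 86.1% | 9.8% |
| 20% v 20% | 0 v 0.5 (extreme) | 85, 85 | 0.175 | 0.52 | 89.1 → 67.6% | 20.4% |

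The reverse pattern, with more of the worse outcomes removed from the control arm, biases the other way and could hide a real reduction.

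**Check with skewed data.** Opioid use is unlikely to be normal, so the cases were also simulated with lognormal outcomes (log-SD 0.8, assumed), a Wilcoxon test and 20,000 trials each. The per-protocol false rates differ from the table by at most 0.7 percentage points (9.1% against 9.8% in the 10% v 10% case). The as-randomised analysis stays at 2.3% to 2.7% throughout, given that outcomes are known for all 106 per arm.

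**The case against.** Per-protocol is an accepted set for equivalence, and the primary endpoint is little affected: in the 5% v 10% case TOST power falls from 93.4% to 93.0–92.2%. No false-equivalence rate was computed, so no wrong primary conclusion has been shown. This stands, and it is why the point centres on Hypothesis 2.1.

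The sizes are also assumed. The only loss figure in the documents is in Sample Size, "Assuming a 20% dropout or withdrawal based upon previous experience, 106 subjects per group will be required", and that is dropout, not per-protocol exclusion. Patients who leave no score are missing from an as-randomised analysis too. With one block under a standardised technique, true deviations could be few: at 2% v 4% excluded (also an assumption) and ρ of 0.3 to 0.5, the same formula gives a shift of 0.04 to 0.06 points and a false rate of 3.1% to 3.5%. This stands as a limit on the size.

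A concomitant procedure may be driven by anatomy or prior planning, with no evident reason to differ by arm. The time of randomisation is not stated, and some cases could be recognised before the block. With equal rates and equal correlation there is no bias. All of this is fair: the documents make the mechanism possible but do not show that it operates.

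None of it removes the gap. If exclusions prove rare or balanced, the two sets will agree and the second analysis will show it. If not, the plan as written has no means of revealing it.

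**Conclusion.** The concern holds. Per-protocol is the sole and undefined analysis set, and it is applied to a directional hypothesis and other difference outcomes for which it is not a sound sole choice. The text of the plan establishes this without the illustration.

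The likely effect on the pain equivalence tests is small. For Hypothesis 2.1 the false-positive rate in the liposomal arm's favour rises from 2.5% to roughly 4–5% in the milder cases tabulated and to about 7% at 10% v 20% with ρ = 0.5. The larger entries need very unequal correlations between arms. All these sizes rest on assumed exclusion rates and correlations. The plan should be corrected, but the per-protocol equivalence analysis of the primary endpoint remains valid.

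**What to change.** Replace the per-protocol sentence in the Analytical Plan with text to this effect:

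> Hypothesis 2.1 and the other outcomes compared for a difference (one-week opioid use, nausea and vomiting, length of stay, satisfaction, pain at 48 h and 72 h) are analysed primarily in all randomised patients who undergo the study operation, by assigned group and regardless of deviations after the block, including a concomitant procedure added during the operation. The per-protocol set is a sensitivity analysis for these outcomes. The equivalence tests of 24 h and 12 h pain are reported in both the per-protocol and the as-randomised sets; any disagreement is reported and limits the equivalence conclusion. Per-protocol exclusions are fixed in writing and applied by someone unaware of assigned group before outcome data are examined. Patients randomised but not operated on are counted and reported by arm.

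Handling of missing scores is a separate point and needs its own text.

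The cost is a second analysis run and a short written list of exclusions, with no extra patients. In-hospital opioid data for patients who deviate should be obtainable, since the plan already states "Data will also be collected from patient electronic charts". The downside is that the equivalence claim is less firm if the two sets disagree.
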